9.4 Definition of Dose-Limiting Toxicity (DLTs)

The period of DLT monitoring will be 6 weeks beginning from the first durvalumab dose administered. Patients who are removed from the study for reasons other than DLT prior to the administration of the first Thyrogen injection will be replaced with another subject. Patients who do not complete the 6 week period of monitoring beginning from the first durvalumab dose for reasons other than DLT will also be replaced. Grading of DLTs will follow the guidelines provided in the Common Terminology Criteria for Adverse Events (CTCAE) version 4.0.

If >1 of the first 3 patients or >2 of the first 6 patients develop a DLT related to durvalumab, further accrual to the study will be halted. If this threshold is not crossed, 11 patients in total will be accrued to the pilot study.

With the exception of specific AEs discussed below, a DLT will be defined as any Grade 3 or higher toxicity that occurs during the DLT evaluation period felt to be possibly, probably, or definitely related to durvalumab. For >Grade 3 adverse events that occur in patients during the DLT monitoring period, investigators must use their discretion to decide if the adverse event is a DLT (e.g., alkaline phosphatase elevation in the context of known progression of hepatic and/or bone metastases might be attributed to progression of disease per investigator discretion).

Any AE requiring discontinuation of durvalumab will also be considered a DLT. Durvalumab-related AEs that occur during the 6-week DLT evaluation period and delay the administration of the second durvalumab dose and/or Thyrogen/RAI therapy by more than two weeks will also be considered DLTs.

Toxicity that is clearly and directly related to the primary disease or to another etiology is excluded from this DLT definition.

The following will be DLTs:

- Any Grade 4 immune related Adverse Event (irAE)
- Any \geq Grade 3 colitis
- Any \geq Grade 3 noninfectious pneumonitis
- Any \geq Grade 3 nephritis or renal dysfunction (elevated serum creatinine)
- Any Grade 2 pneumonitis that does not resolve to \leq Grade 1 within 3 days of the initiation of maximal supportive care
- Any Grade 3 irAE (excluding colitis, pneumonitis, thyroiditis, or nephritis) that does not downgrade to Grade 2 within 3 days after onset of the event despite optimal medical management, including systemic corticosteroids, or does not downgrade to \leq Grade 1 or baseline within 14 days

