14.0 BIOSTATISTICS

The primary objective of this pilot study will be to assess the safety of administering durvalumab in combination with Thyrogen-stimulated RAI therapy in patients with recurrent/metastatic thyroid cancer. The period of dose limiting toxicity (DLT) monitoring will be 6 weeks beginning from the first durvalumab dose. Definitions for DLT are in Section 9.3. Subjects who are removed from the study for reasons other than DLT prior to the administration of the first Thyrogen injection will be replaced with another subject. Patients who do not complete the 6 week period of monitoring beginning from the first durvalumab dose for reasons other than DLT will also be replaced. If >1 of the first 3 patients, or >2 of the first 6 patients, develop DLT related to durvalumab, further accrual to the study will be halted. If this rule is not met, we plan to accrue 11 patients in total to this pilot study (see table below). All toxicities will be graded according to CTCAE v4.0.

Number of DLTs to stop in first 3 patients	Number of DLTs to stop in first 6 patients	Number of DLTs to stop in all 11 patients	Acceptable toxicity rate (H0)	Unacceptable toxicity rate (H1)	Type I error rate	Power
>1	>2	>2	0.10	0.35	0.101184466	0.80748277

Secondary objectives will be determining the best overall response rate (BOR; CRs plus PRs per RECIST v1.1 criteria) and progression-free survival (estimated using Kaplan-Meier methodology with time origin at the start of the treatment; PFS). For PFS, patients will be followed until progression of disease or death, whichever come first. Patients who continue treatment beyond initial investigator-assessed, RECIST 1.1-defined progression, and are subsequently removed from study within the

next radiographic assessment for progression, will be considered to have investigator-assessed progressive disease at the time of the initial progression event.

Exploratory objectives:

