Intratumor heterogeneity analysis: Recently we have developed a technique to characterize the intratumor genetic heterogeneity of tumors based on sequencing data³². Using copy number and mutational data, our computational pipeline infers subclonal populations in tumors. Here, we propose to characterize the evolution of tumors under the selective pressure of rhTSH-stimulated RAI and durvalumab treatment, and examine subclonal expansions that are associated with an immune escape phenotype, by comparing the subclonal architecture of pre- and post-treatment samples.

PBMCs: In addition to the research biopsies, peripheral blood samples will be collected serially for flow cytometry to evaluate changes in T cell subsets at different time points of therapy.

Biostatistical analysis: Proportions of T cell subsets will be summarized at each time point and plotted to reveal any trend.

cfDNA: Collected cfDNA will be analyzed to detect and quantify total cfDNA and the amounts of tumor driver oncogenes (BRAF mutations, RAS mutations, etc...) or other gene mutations present

as appropriate. *Biostatistical analysis*: Changes in these parameters that occur with therapy will be analyzed by graphical method.

Accrual to the trial is anticipated to be approximately 1 patient per month.

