17.3 Serious Adverse Event (SAE) Reporting

An adverse event is considered serious if it results in ANY of the following outcomes:

- Death
- A life-threatening adverse event
- An adverse event that results in inpatient hospitalization or prolongation of existing hospitalization
- A persistent or significant incapacity or substantial disruption of the ability to conduct normal life functions
- A congenital anomaly/birth defect
- Important Medical Events (IME) that may not result in death, be life threatening, or require hospitalization may be considered serious when, based upon medical judgment, they may jeopardize the patient or subject and may require medical or surgical intervention to prevent one of the outcomes listed in this definition

Note: Hospital admission for a planned procedure/disease treatment is not considered an SAE.

SAE reporting is required as soon as the participant starts investigational treatment/intervention. SAE reporting is required for 30-days after the participant's last investigational treatment or intervention. Any events that occur after the 30-day period and that are at least possibly related to protocol treatment must be reported.

Please note: Any SAE that occurs prior to the start of investigational treatment/intervention and is related to a screening test or a procedure (i.e., a screening biopsy) must be reported.

All SAEs must be submitted in PIMS. If an SAE requires submission to the HRPP office per IRB SOP RR-408 'Reporting of Serious Adverse Events', the SAE report must be sent to the IRB within 5 calendar days of the event. All other SAEs must be submitted within 30 calendar days of the event.

The report should contain the following information:

- The date the adverse event occurred
- The adverse event
- The grade of the event

- Relationship of the adverse event to the treatment(s)
- If the AE was expected
- Detailed text that includes the following
 - A explanation of how the AE was handled
 - A description of the subject's condition
 - Indication if the subject remains on the study
- If an amendment will need to be made to the protocol and/or consent form
- If the SAE is an Unanticipated Problem

For IND/IDE protocols:

The SAE report should be completed as per above instructions. If appropriate, the report will be forwarded to the FDA by the IND office.

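### The DLT limits at 3 and 6 patients carry no accrual pause, so at the planned rate patients 4 and 7 may be dosed while a limit can still be crossed (cheap improvement)

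*Combined protocol and SAP*

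**What the plan says.** Section 14.0 sets limits of more than 1 DLT in the first 3 patients and more than 2 in the first 6; if more patients than that "develop DLT related to durvalumab, further accrual to the study will be halted". Sections 1.0, 4.2 and 9.4 repeat the rule, and 9.4 adds "If this threshold is not crossed, 11 patients in total will be accrued to the pilot study". The table in 14.0 also has a column headed "Number of DLTs to stop in all 11 patients", with a limit of more than 2.

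On timing, Section 14.0 states "The period of dose limiting toxicity (DLT) monitoring will be 6 weeks beginning from the first durvalumab dose" and, at its end, "Accrual to the trial is anticipated to be approximately 1 patient per month". On replacement, Section 9.4 states "Patients who do not complete the 6 week period of monitoring beginning from the first durvalumab dose for reasons other than DLT will also be" (the sentence ends by saying that another subject takes their place). Section 4.3 places Thyrogen and RAI in Week 3 of Cycle 1, and Section 5.2 describes this as two weeks after the first durvalumab dose.

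None of these sections pauses enrolment after patient 3 or patient 6, or sets a minimum interval between patients. Section 16.3 describes institutional monitoring in general terms and says nothing about accrual at the two looks.

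**The concern.** The looks at 3 and 6 exist to limit how many people receive an untested combination if it proves too toxic. The window (6 weeks) is longer than the planned interval between patients (about 4.3 weeks). Unless enrolment waits, the next patient starts while the last patient of the group being judged is still under observation. If that last patient then has the DLT that crosses the limit, someone whom the look was meant to protect has already been dosed. Safety is the primary objective, so the plan should say what happens in this interval.

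**Working it through.** **1. The plan's own figures.** The rule stops if there are at least 2 DLTs in 3 patients, at least 3 in 6, or at least 3 in 11, with complete data at each look. Exact binomial enumeration gives:

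- rate 0.10: 0.0280 + 0.0075 + 0.0657 = 0.1012 (plan: 0.101184466)
- rate 0.35: 0.2817 + 0.1368 + 0.3890 = 0.8075 (plan: 0.80748277)

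Both reproduce. They assume complete DLT data on exactly 3 and 6 patients.

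**2. Calendar at regular accrual.** One month is taken as 30.4 days and patient 1 is dosed on Day 0.

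| Patient | First dose (day) | Window closes (day) |
|---|---|---|
| 1 | 0 | 42 |
| 2 | 30.4 | 72.4 |
| 3 | 60.8 | 102.8 |
| 4 | 91.2 | |
| 5 | 121.6 | 163.6 |
| 6 | 152.0 | 194.0 |
| 7 | 182.4 | |

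The overlap at each look is 42 − 30.4 = 11.6 days (1.65 weeks). Only the last patient's window is still open. Under regular spacing the overlap disappears only below 30.4/42 = 0.72 patients per month. With random (Poisson) arrivals at the planned mean rate, 42/30.4 = 1.38 patients on average start within patient 3's window, and at least one does with probability 1 − exp(−1.38) = 0.75.

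**3. When the open window matters.** Let p be the true DLT rate and q = 1 − p.

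- First limit: it is undecided when patient 4 is dosed only if exactly one of patients 1 and 2 had a DLT, with probability 2pq. This is 2 × 0.35 × 0.65 = 0.455 at p = 0.35, and 2 × 0.10 × 0.90 = 0.18 at p = 0.10.
- Second limit: exactly two DLTs in patients 1 to 5, with no more than one in patients 1 to 3. The probability is 3pq² × 2pq + q³ × p². At 0.35: 0.4436 × 0.455 + 0.2746 × 0.1225 = 0.24. At 0.10: 0.243 × 0.18 + 0.729 × 0.01 = 0.05.

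**4. Chance that a patient is dosed before a late crossing.** The documents give no onset times. Assume onset uniform over 42 days, so a DLT falls in the last 11.6 days with probability 11.6/42 = 0.276.

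- First limit, 0.35: 0.455 × 0.35 × 0.276 = 0.044. As a share of all first-limit crossings: 0.044/0.2817 = 16%.
- First limit, 0.10: 0.18 × 0.10 × 0.276 = 0.005.
- Second limit, 0.35: 0.2355 × 0.35 × 0.276 = 0.023.
- Second limit, 0.10: 0.0510 × 0.10 × 0.276 = 0.001.

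**5. Sensitivity.** With random arrivals, simulation puts the share of first-limit crossings at 0.35 that come after patient 4 is dosed at about 35%. If onset is confined to weeks 3 to 6, after RAI, the fraction in step 4 becomes 11.6/21 = 0.552, and the share under regular spacing becomes 0.455 × 0.35 × 0.552/0.2817 = 31%.

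**6. RAI.** At regular spacing patient 4's RAI is due no earlier than about Day 91 + 14 = 105, after patient 3's window closes on Day 103. Patient 7's is due no earlier than about Day 182 + 14 = 196, after Day 194.

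**The case against.** The strongest reply is that the limits are usually already decided. By Day 91 patients 1 and 2 have finished their windows, and two DLTs between them would have stopped accrual. With none between them, patient 3 alone cannot cross the limit. There is also a single fixed regimen, so a later patient is not exposed to an escalated dose. The accrual rate is only approximate, and silence about a hold does not rule one out in institutional monitoring arrangements set at activation (Section 16.3). All of this stands, and it is why the effect is small. It does not close the gap, because nothing in the document requires the pause.

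Three stronger readings are tempting and are not supported:

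- **That a limit can be crossed only after a further patient has been dosed.** Under regular accrual and uniform onset, about 84% of first-limit crossings at 0.35 are seen before patient 4 starts.
- **That the extra patient will have received RAI, which cannot be withdrawn.** At regular accrual, RAI falls after the look closes. Earlier exposure needs arrivals faster than the regular monthly schedule.
- **That the reporting deadline in Section 17.3, "All other SAEs must be submitted within 30 calendar days of the event", delays the look.** That is a limit for submitting SAE reports. DLTs are judged by investigators under the monitoring in Sections 9.4 and 10, and nothing makes the DLT count wait for SAE submission.

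**Conclusion.** The point holds as a cheap improvement. The written rule does not prevent patient 4 or patient 7 from being dosed while the corresponding limit is still reachable, and at the planned rate the overlap is expected, though not certain. At the rate that the plan calls unacceptable (0.35), the consequence is a patient dosed ahead of a late crossing in roughly 1 trial in 23 at the first look (4.4%) and 1 in 44 at the second (2.3%). At the acceptable rate (0.10) it is rare. These figures rest on regular 30.4-day spacing, uniform DLT onset and no replacements. Random arrivals, or DLTs clustering after the Week 3 RAI, raise them, and replacing a non-evaluable patient can push a look later. Provided the limits are still applied to the first 3 and first 6 patients, the type I error and power are not in question. What is at stake is protection of the next patient at each look.

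**What to change.** Add to Sections 9.4 and 14.0 wording such as:

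> After 3 (and again after 6) evaluable or potentially evaluable patients have started durvalumab, no further patient other than a replacement for a non-evaluable patient will start until those patients have completed the 6-week DLT period or had a DLT, unless the halting limit can no longer be reached by patients still in the window.

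The exception for replacements is needed because otherwise a replacement for one of the first three would be barred by the hold that he or she is required to complete.

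The cost at the planned rate is 6 − 4.35 = 1.65 weeks per look, at most about 3.3 weeks over both. There is no wait when the limit is out of reach. At a DLT rate of 0.10 the first hold applies with probability 0.18, an average wait of at most 0.18 × 11.6 = 2.1 days. No patients or procedures are added, and the error rates stay at 0.1012 and 0.8075. If the sponsor prefers not to pause, the protocol should state how many patients may be dosed past each look.

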Taken together, our central hypothesis is that in addition to putative neoantigens, nonmutated protein immunogens contribute to thyroid cancer foreignness, and can be upregulated/released to optimize antigenic T cell priming to enhance the efficacy of PD-1 pathway directed therapy.

Rationale for combining TSH-stimulated RAI therapy with PD-1 pathway blockade: Here we propose using TSH-stimulated RAI therapy to upregulate the expression and release of nonmutated proteins and putative neoantigens to amplify the therapeutic efficacy of PD-1 pathway blockade for the treatment of RAI-avid recurrent/metastatic thyroid cancers. TSH stimulation globally increases the expression of thyroid-specific genes in DTCs. This effect extends to those genes which mediate RAI avidity, a property that is routinely exploited clinically for diagnostic and therapeutic purposes when recombinant human TSH (rhTSH; Thyrogen (Genzyme)) is administered to patients in order to optimize RAI uptake in normal and malignant thyroid tissue. Consistent with this mechanism of action, rhTSH has been reported to boost circulating TG levels on average ~3 fold or higher²⁷. Additionally, dramatic increases in TG have also been documented after RAI administration²⁸⁻³⁰, consistent with RAI-induced thyroiditis and tumor lysis leading to the release of thyroid antigens. In this way, RAI may boost PD-1 pathway directed therapies in a manner similar to the “abscopal effect” described with radiation therapy, except that systemically administered RAI may optimize antigen release from not just one irradiated site, but multiple tumor sites, unmasking the full complement of neoantigens accompanying disease heterogeneity. Hence, rhTSH-stimulated RAI may be an effective approach for optimizing nonmutated protein and neoantigen release to optimally prime the T cell response simulated by PD-1 pathway blockade, which we propose to achieve with the PD-L1 targeting antibody durvalumab (AstraZeneca).

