DNA and RNA will be extracted from frozen samples and/or paraffin tissue. The research peripheral blood sample collected on the study will be used as a control, matched normal sample (microdissection of normal tissue in the tumor samples may also be used for this purpose). DNA will be submitted for next generation sequencing, possibly whole exome or whole genome sequencing. The specific assay that will be employed to analyze for genomic alterations will be dependent upon the technology available at the time of analysis. Comparisons of DNA between tumor and normal tissue (from the research blood draw) will be performed as appropriate, thus generating germline sequence data. There is no intention to analyze the germline data beyond

utilizing it as a normal control for the tumor tissue analysis, and generally germline data will not be communicated to the patient. This data will be used to quantitate mutation load and identify candidate neoantigens.

Extracted RNA will be analyzed with RNAseq technology, or alternative assays, depending on technical limitations and assay availability. RNAseq data will be used to define a set of expressed neoepitopes and explore gene expression signatures that may correlate with response. RNAseq data analysis may include:

- Quantification of the following: 1) Markers of the MAPK pathway transcriptional output (e.g. Etv1, Etv4, Etv5, Spry2, Spry4, Dusp6); 2) Genes required for thyroid hormone biosynthesis (e.g. Nkx2.1, Pax8, Foxe1, Tg, Tpo, TshR, Nis, Pendrin, Dio2); 3) PD-L1 expression (PD-L1 expression will also be analyzed by IHC).
- Analysis to characterize tumor (a) immune cell infiltration and (b) immunologic gene signatures.

For patients in whom two serial research biopsies are obtained, evolution of the mutation, neoantigen, and gene expression landscape in pre- and post-treatment samples will be analyzed to gain insights into immunoediting that may occur and infer what epitopes may be critical for efficacy. RNAseq data will also be used to explore changes in the expression of nonmutated thyroid gene expression (e.g. TG, THSR, TPO, etc...) with therapy for the same purpose. The same data can be analyzed to evaluate how immune cell tumoral infiltration and immunologic gene signatures may change with therapy.

Frozen tissues from the research biopsy may be evaluated for relevant protein targets by Western blot or other proteomic assays that may be available at time of analysis.

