Mutation burden, neoantigen landscape, and immunoediting analysis: While the low DTC mutation burden implies a low likelihood of neoantigen formation, neoantigen analysis has never been conducted for DTC. Whole-exome sequencing data will be analyzed using the neoepitope bioinformatics pipeline developed by [name] group. Mutation calling is performed by analyzing FASTQ files with four mutation callers and filtering by allelic frequency, call quality and other empiric measures. Mutations are validated with an orthogonal next-gen sequencing panel. Candidate neoantigens are identified based on peptide sequences and predicted binding to patient-specific MHC Class I alleles. RNAseq data will be used to define a set of expressed neoepitopes and explore gene expression signatures that may correlate with response. Evolution of the mutation, neoantigen, and gene expression landscape in pre- and post-treatment samples will be analyzed to gain insights into immunoediting that may occur and infer what epitopes may be critical for efficacy. RNAseq data will also be used to explore changes in the expression of nonmutated thyroid gene expression (TG, THSR, TPO, etc...) with therapy for the same purpose. *Biostatistical analysis:* Categorical pre- and post-treatment measures will be summarized by 2-by-2 tables; continuous pre- and post-treatment measures will be summarized by mean and standard deviation of the change as well as graphical method.

Immune cell infiltrate and immunologic gene signature analysis: Tumor RNAseq data will be used to analyze changes in (a) immune cell infiltration and (b) immunologic gene signatures with therapy. First, we will estimate the relative infiltration levels of individual immune cell populations in tumor samples using two computational approaches. The first was developed by [name] and [name] at MSK which uses single set enrichment analysis (ssGSEA) to determine the abundance of T cell and other immune cell populations in the tumor microenvironment³². A related but alternative approach uses support vector regression to model cellular populations based on a reference expression matrix³³. These techniques provide efficient and accurate alternatives to flow cytometry sorting. In addition, RNAseq data permits quantification of related immunologic gene expression signatures such as IFNy signaling, granzyme B, and antigen presenting machinery genes.

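### The exploratory immunoediting analysis has no neutral comparator, so pre/post change in tumours treated with both RAI and durvalumab cannot by itself separate immune selection from RAI killing or sampling loss

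*Combined protocol and SAP*

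**What the plan says.** Section 14.0 (mutation burden, neoantigen landscape and immunoediting) says the pre- and post-treatment mutation, neoantigen and expression data will be "analyzed to gain insights into immunoediting that may occur and infer what epitopes may be critical for efficacy". Section 9.5 repeats the aim for patients with two biopsies: their data "will be analyzed to gain insights into immunoediting that may occur and infer what epitopes may be critical for efficacy". Changes in nonmutated thyroid genes (TG, TSHR, TPO) are to be explored for the same purpose.

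The statistics for these measures are descriptive: "Categorical pre- and post-treatment measures will be summarized by 2-by-2 tables", and "continuous pre- and post-treatment measures will be summarized by mean and standard deviation of the change as well as graphical method".

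The heterogeneity paragraph of Section 14.0 follows tumour evolution "under the selective pressure of rhTSH-stimulated RAI and durvalumab treatment" and will "examine subclonal expansions that are associated with an immune escape phenotype, by comparing the subclonal architecture of pre- and post-treatment samples". The immune escape phenotype is not defined.

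On the competing cause, Section 3.0 describes thyroglobulin rises after RAI as "consistent with RAI-induced thyroiditis and tumor lysis leading to the release of thyroid antigens". Section 9.5 places the second biopsy after durvalumab and RAI, in Cycle 2. Section 9.3 prefers the same lesion for both biopsies but does not require it. There is no group given only one of the two agents.

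**The concern.** A mutation present before treatment and absent afterwards may have been removed by T cells. It may also have sat in a clone that RAI killed, or been missed because the second set of cores sampled a different part of the tumour. The last two need no immune recognition. They remain even with the same lesion, fixed timing and purity-corrected data.

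Nothing in the plan asks whether mutations predicted to yield neoantigens are lost more often than mutations that are not. That contrast is the one the existing data could supply to separate immune selection from neutral loss.

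The expression arm has the same weakness. Section 3.0 notes that genes governing RAI avidity are also the thyroid antigens of interest. If RAI preferentially kills avid cells, their expression falls without any T-cell effect.

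At stake is the exploratory aim of naming epitopes that matter for efficacy. Candidates could be produced by RAI or by sampling, from biopsies that are a mandatory burden on patients, subject to safety exemptions.

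**Working it through.** **Figures in the plan.** None is given for this analysis. The only operating characteristics in Section 14.0 belong to the DLT rule (more than 1 of 3, 2 of 6 or 2 of 11). An exact binomial recursion gives 0.10118 at a 10% rate and 0.80748 at 35%, matching the stated figures. This point does not affect them.

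**Inputs.** From the documents: 11 patients planned, pairs only where two biopsies are obtained, and a mutation load below 1 per Mb for most DTCs (Section 3.0). Assumed, because not given: k = 4 to 11 usable pairs, n = 1 to 5 predicted neoantigens per tumour, and q = the probability that a mutation is lost for non-immune reasons.

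**Step 1: chance of at least one lost neoantigen with no immune selection.** P = 1 − (1 − q)^(k·n).

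| q | k=4, n=1 | k=6, n=2 | k=11, n=5 |
|---|---|---|---|
| 0.01 | 1 − 0.99^4 = 3.9% | 11.4% | 42.5% |
| 0.05 | 18.5% | 1 − 0.95^12 = 46.0% | 94.0% |
| 0.10 | 34.4% | 71.8% | 99.7% |
| 0.20 | 59.0% | 93.1% | about 100% |

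Over the 16 combinations of k in {4, 6, 8, 11} and n in {1, 2, 3, 5}, P exceeds 50% in none at q = 0.01, 9 at q = 0.05, 14 at q = 0.10 and all 16 at q = 0.20. Setting P = 0.5 gives q = 1 − 0.5^(1/(k·n)): 0.159 for 4 candidates in total, 0.056 for 12, 0.031 for 22 and 0.0125 for 55.

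**Step 2: subclones.** If a neutral shift occurs in a fraction s of patients, the chance of seeing at least one is 1 − (1 − s)^k. For s = 5% to 30% this is 19% to 76% with 4 pairs and 43% to 98% with 11.

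**Step 3: does an internal comparator help?** Neoantigen losses were compared with losses of the other mutations in the same tumour, using an exact conditional test stratified by patient (one-sided 5%). There were 1,500 simulated trials per null scenario and 800 per power scenario. Power is for a neoantigen loss rate 20 percentage points above q.

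| Pairs | Mutations / neoantigens per tumour | q | Any loss, no selection | False positives with comparator | Power |
|---|---|---|---|---|---|
| 4 | 15 / 1 | 0.05 | 18.5% | 1.1% | 22% |
| 6 | 15 / 2 | 0.10 | 71.7% | 2.6% | 41% |
| 6 | 15 / 2 | 0.10, varying by patient | 66.0% | 1.9% | 47% |
| 6 | 15 / 2 | 0.20 | 92.4% | 2.5% | 35% |
| 11 | 15 / 2 | 0.10 | 90.4% | 2.2% | 68% |
| 11 | 30 / 5 | 0.20, varying by patient | about 100% | 2.9% | 92% |

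**Step 4: power for a threefold odds of loss.**
- 10 mutations, 20% neoantigens, 5% loss: 16% with 6 pairs and 21% with 9.
- 20 mutations, 20% neoantigens, 5% loss: 29% and 41%.
- 30 mutations, 30% neoantigens, 10% loss, by label permutation: 72% to 79% with 6 pairs and 88% to 91% with 9. The higher figure in each range is for loss clustered by clone. False positives were 2.1% to 2.8%.

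**The case against.** The plan is cautious and has more in it than two lists of mutations. It speaks of editing that may occur and epitopes that may matter. Candidates are limited to predicted MHC class I binders, RNAseq is used to define those expressed, and calls are validated on an orthogonal panel. RAI is named as part of the selective pressure, and the subclone work is confined to those it would "examine subclonal expansions that are associated with an immune escape phenotype". Section 9.5 adds ex vivo immunogenicity assays on PBMCs, aimed at antigens critical for efficacy.

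All of that stands, but none of it supplies the missing control. Validation shows that a call is real, not why it later disappeared. Binding and expression filters define candidates without a reference set. The escape phenotype has no definition. The PBMC assays are a genuine functional check, but they have no stated criteria and are not tied to the immunoediting inference. Immunogenicity also does not show that a lost mutation was removed by T cells.

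A reader might infer that the plan counts any pre/post change as immunoediting. It does not: no trigger, threshold or test is stated.

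The comparator has limits too. It assumes that, without immune selection, neoantigen and other expressed coding mutations are equally likely to be lost. It says nothing about nonmutated antigens, and an overall excess would not show which epitope matters.

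**Conclusion.** The point holds as one of identifiability. Pre/post change in tumours that have had both agents, with no neutral comparator, cannot separate immune selection from RAI killing or sampling loss. That conclusion does not depend on any assumed number.

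The size does. If loss of a predicted neoantigen is read as a signal, the chance of at least one with no immune selection is about 4% to about 100% for loss rates of 1% to 20%, 4 to 11 pairs and 1 to 5 neoantigens per tumour. It exceeds 50% in many of these settings.

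The stronger statement, that the inference would give a false signal in most datasets, is not supported. The documents give neither the loss rate, the number of usable pairs nor the neoantigen count, and the low mutation load they cite pulls the figure down.

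Priority is low. The objective is exploratory, and the DLT rule, BOR and PFS are unaffected.

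**What to change.** Add to Section 14.0, with matching text in Section 9.5:

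> Loss of predicted, expressed neoantigen mutations will be compared with loss of other expressed coding mutations in the same biopsy pair, stratified by patient (exact or label-permutation test). Mutation-based evidence will be described as consistent with immunoediting only if neoantigen loss exceeds this internal reference. Individual lost epitopes, subclonal expansions and changes in nonmutated thyroid gene expression (TG, TSHR, TPO) will otherwise be reported descriptively as change under RAI plus durvalumab and labelled hypothesis-generating, alongside the ex vivo PBMC immunogenicity results (Section 9.5).

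Pairs taken from different lesions should be flagged. Where counts allow, matching on baseline clonal fraction would make the reference fairer.

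The cost is wording and a little analysis, since the reference mutations come from the same exome data. The price is a more cautious conclusion: with few pairs or few mutations power may be only about 15%, and the result may be that there is no evidence of editing.
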